5.3 LIFESTYLE CONSIDERATIONS

N/A

5.4 SCREEN FAILURES

Screen failures are defined as participants who consent to participate in this study but are not subsequently entered in the study. This may occur if an index participant does not successfully recruit two network members within the allotted time period, or he does not attend the first intervention session. An index participant who does not meet the criteria for participation in this trial (screen failure) because of meeting one or more exclusion criteria may be considered for rescreening if the second group for the cluster has not yet been filled. Only index participants who identified more than 2 potential network recruits during screening will be allowed to replace network recruits who failed screening. Rescreened participants will be assigned the same participant number as for the initial screening.

5.5 STRATEGIES FOR RECRUITMENT AND RETENTION

The study will enroll a total of 420 male Tajik migrant MWID including 140 index participants (MASLIHAT or control intervention) and 280 IDU network members. Based on pilot study experience, since recruitment materials will specify the requirements for participation, nearly all men who present for screening will meet the criteria for enrollment. We anticipate screening up to 150 MWID for participation as index participants, and up to 300 MWID for participation as network members.

Timing for recruitment. Recruitment of index participants (70 MASLIHAT peer educators and 70 control group participants) will take place throughout the intervention/baseline data collection period (18 months) through referrals from the Tajik diaspora organizations and recruitment at the 6 worksites and 4 bazaar sites until sample requirements for 140 index participants are met. Network member recruitment (n=280) will occur through referral by the index participants. As with the pilot study, only

index participants who successfully recruit two eligible network members will participate in the interventions. Recruitment will be conducted intensively at two sites at a time, one assigned to the intervention and the other to the control. We will recruit from these sites until we have filled two groups of 5 to 7 eligible participants (each having successfully recruited 2 network members). Groups will be closed to new members after the first session. When we have filled 2 groups for each site in the pair, the recruitment team will move on to the next pair of sites. We will run four intervention groups each quarter (2 MASLIHAT and 2 TANSIHAT) over a period of 18 months (20 groups total).

Sample composition. The sample will be entirely composed of Tajik male labor migrants working in Moscow. No women are included in the research, as few women travel to Moscow for work. Also the study focuses on injection drug use which is practiced primarily by Tajik males. All study participants are Tajik nationals working in Moscow. Most are likely to be ethnic Tajiks, but members of Tajik ethnic minority groups (Uzbeks, Pamiris, Tatars, and Belarusians) also will be eligible to participate. Children under 18 will not be included in the research, as Tajik migrant workers are required by law to complete secondary school. In addition, injection drug use among children under 18 in Tajikistan is extremely unlikely. Through NGO referrals and worksite/bazaar recruitment, we will be able to sample migrant MWID originating from all five regions of Tajikistan.

Recruiting intervention participants. Recruitment of intervention participants will be conducted by outreach at twelve sites including 2 diaspora organizations, 4 bazaars, and 6 other worksites located near metro stations in districts with substantial migrant settlement. We will recruit 10 to 14 Tajik migrant men who inject drugs (MWID) at each of these sites to participate in the MASLIHAT (n=70) or control (n=70) intervention. Participants will be assigned to condition based on recruitment site. Recruitment sites will be pair matched and randomly assigned to a study arm, with one site of each pair assigned to MASLIHAT (see Section 6.3 for details). Recruiters will be blinded to site assignment. Recruitment materials (flyers, cards) will include a code to identify the recruitment site. When a potential participant contacts the research staff for pre-screening, he will be asked for this code.

Recruiting from diaspora organizations. The Moscow site PI ([name]) and the Chair of the Tajik Union ([name]) will meet with leaders of the NUR and Selart Tajik diaspora organizations to explain the study and discuss the recruitment plan. Diaspora organization staff will inform men about the study and the requirements for participation, and distribute a handout that includes contact information. They will encourage visitors to refer men they know who appear to meet the study's eligibility criteria to contact PRIZMA for screening and possible participation.

Recruiting from worksites. Most Tajik male migrants in Moscow work either in bazaars or in construction. The PRIZMA research team has experience in recruiting Tajik migrants from worksites for participation in research. We have selected four bazaars and six other worksites near metro stations as recruitment sites. Workers at the bazaars are organized in brigades, each consisting of 5 to 15 workers. The number of brigades within bazaars varies from 5 to 150. [name] and [name] will meet with diaspora organization leaders to make connections with Tajik brigade leaders and worksite managers. They will meet with the brigade leaders and worksite managers to explain the purpose of the study and make plans for distribution of study information. The brigade leaders and worksite managers will distribute cards with study information, eligibility criteria, and contact details to Tajik migrants.

Recruiting network members. Men who call the PRIZMA center will be screened for eligibility by the project coordinator and given an appointment for the enrollment visit. At the enrollment visit the project coordinator will explain the study requirements and confirm eligibility. Eligibility will be confirmed by inspecting for injection marks, or if marks are not visible, asking the subject about the injection process using a series of questions designed to identify PWID (SATHCAP injection screener). After completing the

informed consent process and confirming their willingness to recruit two other Tajik migrant MWID for interviewing, index participants will be given two coupons to recruit network members who meet the study criteria for interviews. Network members must meet the same criteria as intervention participants but also: 1) have injected drugs at least once in the last 30 days; and 2) be someone whom the index participant sees at least once a week. When network members present for enrollment, the project coordinator will verify network member eligibility and confirm the identity of the index participant who made the referral.

Retention. Participants will be enrolled only if they expect to remain in Moscow for the next 12 months, and they will be asked to notify the PRIZMA office if they are returning to Tajikistan prior to the study completion. Participant tracking and participant retention will build on successful strategies used by the investigators in achieving high follow-up rates with PWID or migrant populations in prior studies. One challenge of studying migrants is that they can disappear without warning due to legal difficulties or an unexpected reason to return to home. Many are without permanent residence. We will use a series of strategies to retain participants over time. Key contact information (work, residence, friends/family, regular “hang-outs”) will be collected at intake for follow-up interviewing and updated at each follow-up contact. Participants will be contacted by phone or other preferred arrangements prior to each MASLIHAT session or interview as a reminder. If a participant cannot be reached by phone or other contact methods after missing an appointment, the Moscow Project Coordinator will visit the person’s last known address or locations where he typically frequents, and inquire with his recruiter or network members.

Compensation: Participants will receive the customary compensation in Moscow of \$20.00 for each interview completed. Intervention participants will also receive transit passes to attend the group sessions at the PRIZMA Research Center.

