9.2 SAMPLE SIZE DETERMINATION

We estimated power allowing up to 10% attrition among intervention participants and up to 15% attrition among network members. Power calculations were computed using PASS software and considering effects observed in the pilot study.

We expect to see large reductions in syringe sharing and condomless sex in the MASLIHAT intervention group, and little change in these behaviors in the control group. In the pilot study, syringe sharing decreased from 52% at baseline to 0% at six months, and condomless sex decreased from 35% at baseline to 1% at six months. For binary outcomes, we computed Mixed Models Tests for Two Proportions in a 3-Level Hierarchical Design (Level-3 Randomization), with an intracluster correlation of 0.05 and alpha=.01. We computed power for outcomes ranging from 0.30 to 0.50 for the control group, and 0.05 to 0.15 for the MASLIHAT intervention group, and with 10, 20 or 30 subjects per cluster, representing intervention participants, network members, and the complete sample. We will have at least 80% power to detect predicted changes in condomless sex, and over 90% power to detect predicted changes in syringe sharing. In the larger sample, we will have adequate power to detect effects even if they are not as large as anticipated.

The intervention also targets alcohol use and in the pilot study, days of alcohol use in the past month decreased from 5 to 2, with $b/SE = -6.52$, yielding a Cohen's d effect size of -0.69. We estimated power by computing Mixed Models Tests for the Slope Difference in a 3-Level Hierarchical Design with Fixed Slopes (Level-3 Randomization), with subject $icc=0.30$ and $alpha=0.01$, for a standardized mean difference (SMD) of 0.50 to 0.70, with cluster sizes of 10, 20. and 30. For the intervention participants, we will have at least 80% power to detect a $SMD=0.70$; for network members we will have at least 80% power to detect a $SMD=0.50$, and for the complete sample we will have at least 80% power to detect a $SMD=0.41$.

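### The stated total of 20 groups contradicts both the quarterly rate and the 12-site design (each gives 24), and the stopping rule lets recruitment close with one randomised pair unused

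*Combined protocol and SAP*

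**What the plan says.** Section 5.5 gives the pace, the period and the total in one sentence: "We will run four intervention groups each quarter (2 MASLIHAT and 2 TANSIHAT) over a period of 18 months (20 groups total"). The same section says that recruitment "will take place throughout the intervention/baseline data collection period (18 months") and continues "until sample requirements for 140 index participants are met". Sites are worked two at a time, one from each arm: "We will recruit from these sites until we have filled two groups of 5 to 7 eligible participants", and then "When we have filled 2 groups for each site in the pair, the recruitment team will move on to the next pair of sites".

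Under the recruitment of intervention participants, Section 5.5 describes "outreach at twelve sites including 2 diaspora organizations, 4 bazaars, and 6 other worksites" and adds: "We will recruit 10 to 14 Tajik migrant men who inject drugs (MWID) at each of these sites". Section 4.1 also gives twelve sites. Section 6.3 pair-matches and randomises all 12, which makes six pairs.

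Section 9.2 computes power "with 10, 20 or 30 subjects per cluster" for index men, network members and both together. It does not state the number of clusters.

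**The concern.** The total of 20 disagrees with the rate and period in its own sentence, and with the number of sites times the groups per site. This is more than a miscount, because 20 groups describe a schedule that staff could actually run. With full groups, five pairs supply all 140 men, at 70 per arm. Nothing in the sequential rule says that the sixth pair must be opened.

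The site is the unit of randomisation. If one pair drops out, the trial has 5 sites per arm instead of 6, and each site is larger. Enlarging sites does not fully replace lost sites when outcomes are correlated within a site.

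**Working it through.** **1. Number of groups (Sections 5.5 and 6.3).**
- Rate × period: 4 per quarter × (18 ÷ 3) quarters = 24.
- Sites × groups per site: 12 × 2 = 24.
- The stated 20 is not reproduced by either route. It arises only as 4 × 5 quarters (15 months, not 18), 10 sites × 2, or 140 ÷ 7.

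**2. Capacity at 5 to 7 men per group.**
- 20 groups hold 100 to 140, so 140 requires 7 in every group.
- 24 groups hold 120 to 168. A total of 140 then means 140 ÷ 24 = 5.8 per group and 140 ÷ 12 = 11.7 per site, inside both stated ranges.

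**3. Earliest stop.** Five pairs give 10 sites × 2 groups × 7 = 140, or 5 × 14 = 70 per arm. The target is then met with the sixth pair unopened.

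**4. Clusters implied by Section 9.2.** After the stated attrition, 140 × 0.90 = 126 index men and 280 × 0.85 = 238 network members remain, 364 in all.

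| Sites | Index | Network | All |
|---|---|---|---|
| 12 | 10.5 | 19.8 | 30.3 |
| 10 | 12.6 | 23.8 | 36.4 |

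The stated 10, 20 and 30 fit 12 sites and not 10.

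**5. Binary outcomes.** The plan used a three-level calculation whose other inputs are not given, so this is a two-level approximation. ICC 0.05 and alpha 0.01 come from Section 9.2; two-sided testing is assumed. With c sites per arm and m men per site:
- effective n per arm = c·m ÷ [1 + (m − 1) × 0.05]
- s1 = √{[p1(1 − p1) + p2(1 − p2)] ÷ n}, and s0 = √{2p̄(1 − p̄) ÷ n}
- lower figure: Φ[(Δ − 2.576·s0) ÷ s1]; upper figure: Φ[Δ ÷ s1 − 2.576]

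Example, 35% versus 10%, full sample:
- 6 sites × 30: n = 180 ÷ 2.45 = 73.5, s1 = 0.0657, s0 = 0.0689. The lower figure is Φ[(0.25 − 0.1775) ÷ 0.0657] = 87% and the upper is 89%.
- 5 sites × 36: n = 180 ÷ 2.75 = 65.5, giving 81–84%. With 36.4 per site it is 82–85%.

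| Comparison | 12 sites | 10 sites |
|---|---|---|
| Condomless sex 35% v 10%, all (30; 36 to 36.4 per site) | 87–89% | 81–85% |
| Condomless sex 35% v 5%, all (same sizes) | 98–99% | 97–98% |
| Condomless sex 35% v 5%, index men (10; 12 to 12.6 per site) | 82–87% | 78–85% |
| Syringe sharing 50% v 5%, index men (same sizes) | at least 99% | at least 98% |

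The 12-site figure for index men agrees with the plan's claim of at least 80% for condomless sex.

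**6. HIV and HCV.** The Hayes–Bennett formula for cluster rates, with the stated CVs of 0.50 (control) and 1 (intervention), one-sided 0.05 and 80% power, is

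c = [+1] + (1.645 + 0.842)² × [(λ0 + λ1) ÷ y + 0.25λ0² + λ1²] ÷ (λ0 − λ1)².

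- HIV, 0.10 v 0.011, y = 30: 6.183 × 0.006321 ÷ 0.007921 = 4.93, or 5.93 with the +1.
- HCV, 0.40 v 0.086, y = 15: 6.183 × 0.079796 ÷ 0.098596 = 5.00, or 6.00 with the +1.

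The plan's detectable ratios therefore reproduce with 6 sites per arm and the +1 term, or equally with 5 per arm and no +1 term. At 5 per arm, with sizes scaled to 30 × 12/10 = 36 and 15 × 12/10 = 18, power at the stated ratios is 76% (HIV) and 74% (HCV) with the +1, and 84% and 82% without it.

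**The case against.** The plan can be carried out at 12 sites, and Section 5.5 says that men will be recruited at each of the twelve, with a minimum of 10. Closing after five pairs would break that sentence and would need every group filled to 7. This stands as far as it goes: stopping at 10 sites is the extreme case and not the evident intention. But 7 per group is also the only way that 20 groups can yield 140 men, so the stated total and the twelve-site sentence cannot both be followed.

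The 20 might instead count only the 6 worksites and 4 bazaars, with the diaspora organisations as referral sources. That explains a possible origin but does not rescue the figure, because Section 5.5 counts the two organisations among the twelve sites and Section 6.3 randomises twelve.

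A reader might infer that the stated power no longer holds. The documents do not support that:
- Under the normal approximation, full-sample power for condomless sex stays above 80% at 10 sites, and syringe sharing is hardly affected. In index men, 35% versus 5% becomes borderline.
- A t reference on sites minus 2 degrees of freedom gives lower figures (35% versus 10%, full sample, unpooled variance: 72% at 12 sites, 61% at 10). But that shortfall already exists at 12 sites, and Section 9.4 sets no such degrees-of-freedom rule.
- The HIV and HCV loss depends on the +1 term, which Section 9.2 does not mention.

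**Conclusion.** The text is wrong as written. The contradiction between 20 and 24 is exact and rests on no assumption. It is also more than clerical, because the group total and the stopping rule together decide how many randomised sites enrol.

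The consequence for power is modest and conditional on recruitment actually ending at 10 sites: about 5 points for condomless sex at 35% versus 10% in the full sample, and about 3 points at 35% versus 5% in index men when site sizes are rounded the same way in both designs. For HIV and HCV the loss is either 4 to 6 points, to below 80%, or leaves power above 80%, according to the formula used. These sizes assume two-sided testing, a two-level model and an unchanged total sample. That Section 9.2 used 12 clusters is inferred from its cluster sizes; the HIV and HCV figures alone cannot separate 6 per arm from 5.

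**What to change.** In Section 5.5, change the total to 24 groups, two at each of 12 sites. Add one sentence saying that recruitment closes only after all six matched pairs have enrolled. Keep 140 index men (70 per arm), groups of 5 to 7, and 10 to 14 men per site; these are mutually consistent at 24 groups. A tighter quota of 11 to 12 per site is not needed, and it could miss the target, since 12 × 11 = 132.

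If 20 groups at 10 sites is what the investigators intend, Sections 4.1, 5.5 and 6.3 must be reconciled to that number and Section 9.2 restated with 5 sites per arm. In either case, Section 9.2 should state the number of clusters.

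The cost of the main fix is one or two sentences in Section 5.5. Twenty-four groups already fit four per quarter over 18 months, so neither the period nor the sample size changes.

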1 PROTOCOL SUMMARY

1.1 SYNOPSIS

Title:	MASLIHAT Intervention for Tajik Male Migrants Who Inject Drugs
Grant Number:	1R01DA050464
Study Description:	
This protocol will test the efficacy of the MASLIHAT peer education HIV prevention intervention for Tajik migrant laborers who inject drugs in the host country, against an attention control. The primary outcomes are self-reported risk behaviors among participants and network members over 12 months following the intervention, including syringe sharing, and sex without condom. Follow-up interviews will be conducted at 3, 6, 9, and 12 months. We will conduct HIV testing at baseline and 12-month follow-up, and HCV testing at baseline and 6- and 12-month follow-up. We expect the MASLIHAT intervention to be associated with greater reduction in injection and sexual risk behavior during follow-up compared with the control condition.

Objectives[*]:	
Primary Objective: Assess the efficacy of the MASLIHAT intervention compared to the TANSIHAT control condition for reducing injection equipment sharing, condomless sex, and heavy alcohol use among intervention participants and among their network members.
 
Secondary Objectives: Assess the efficacy of the MASLIHAT intervention compared to the TANSIHAT control condition for reducing the incidence of HIV and hepatitis C infection among intervention participants and among their network members

Endpoints[*]:	
Primary Endpoint: Reduce the proportion of men sharing syringes or other injection equipment in the past 3 months to 10% or less; reduce the proportion of men engaging in condomless sex in the past 3 months to 10% or less. Reduce the proportion of men engaging in heavy alcohol use in the past 3 months to 10% or less.
 
Secondary Endpoints: Reduce the 12-month incidence of HIV and HCV by 50% compared to the control group.
 
We will enroll a total of 420 male Tajik migrant workers who inject drugs in Moscow, including 140 intervention participants (70 MASLIHAT, 70 control group) and 280 network members recruited by the intervention participants for participation in the assessments.

Phase[*] or Stage:	Phase 2
Description of Sites/Facilities Enrolling Participants:	Participants will be enrolled at PRIZMA Research Center in Moscow, Russia.

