4.2 SCIENTIFIC RATIONALE FOR STUDY DESIGN

We will use a cluster-randomized design to prevent control group contamination due to the nature of the intervention. Because the intervention is designed to reach the participant's social network through peer education activities, individual randomization to condition is not feasible.

The Targeted Application of Network and Social Intervention on Health Assistance for Tajiks (TANSIHAT) program will serve as the control condition. TANSIHAT was adapted from the Healthy Lifestyles for Labor Migrants intervention designed by Drs. [name] and [name] to serve as a control condition in testing an HIV prevention model delivered to Tajik migrants. We expanded the program contents to include TB risk and prevention and organized it to be parallel to MASLIHAT in the number and length of sessions. This program provides relevant health information for Tajik migrant workers and encourages participants to share the information with other migrants, but it does not address HIV/STI risk and prevention, condom use, or drug use. It does address heavy alcohol use which will affect our ability to detect effects on drinking behavior.

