5.2 EXCLUSION CRITERIA

Index participants will be excluded from participation in this study if:

1. they do not successfully recruit 2 network members within the allotted time frame, or
2. they do not attend the first intervention session

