6.1.2 ADMINISTRATION AND/OR DOSING

The MASLIHAT and TANSIHAT interventions will be delivered in 5 weekly small group sessions led by a trained facilitator. Sessions will take place at the PRIZMA Research Center. MASLIHAT sessions include group discussions and interactive role-playing activities to practice the communication and outreach skills. MASLIHAT treatment dosage effects for peer educators will be measured by: (1) total number of sessions attended, and (2) specific sessions attended.

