Interviews: Intervention participants and network members will complete computer-assisted personal interviews (CAPI) at baseline (prior to first intervention session), and at 3, 6, 9, and 12 months post-intervention. All baseline and 12-month interviews will be conducted in a private room at the PRIZMA office; intermediate follow-up interviews may be conducted at the PRIZMA office or at a location selected by the subject. Trained interviewers will administer the 60 to 90-minute questionnaire, using a computer-assisted personal interview (CAPI) system (Qualtrics) to record responses. For the more sensitive questions such as sexual behavior and STIs, the interviewer will instruct the participant to enter his responses. The CAPI system will ensure proper administration of skip sequences. For quality control purposes, 20% of interviews will be randomly selected to be audiotaped, and half of these audiotapes will be reviewed by [name] or [name] for quality assurance. Using electronic data capture and requiring timely data uploads will allow the data manager to monitor research progress and conduct quality control checks. The questionnaires were developed and tested with members of the population using cognitive interviewing (CI).⁶² Translations were validated using "back translation" with a member of the study population.

Self-report Measures

Background measures. The baseline interview includes measures of basic sociodemographic variables (education, marital status, migration history, religion), community involvement/social activities, and health (general health, STIs). The follow-up interviews also collect self-reported STIs since last interview.

Outcome measures. Primary outcome measures are syringe sharing in the past 3 months, and vaginal or anal sex without a condom in the past 3 months. Other measures include syringe cleaning methods, and the Alcohol Use Disorder Identification Test (AUDIT)⁶³ to assess alcohol consumption and alcohol-related problems at each time point.

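### Section 5.5 specifies reminder contacts before MASLIHAT sessions and interviews but none before sessions of the attention control, TANSIHAT; the rule should name both programmes

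*Combined protocol and SAP*

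**What the plan says.** The Synopsis (1.1) describes a test of MASLIHAT "for Tajik migrant laborers who inject drugs in the host country, against an attention control". Section 4.2 says that the team extended the control programme, TANSIHAT, and "organized it to be parallel to MASLIHAT in the number and length of sessions". Section 6.1.2 gives both arms the same format: "The MASLIHAT and TANSIHAT interventions will be delivered in 5 weekly small group sessions led by a trained facilitator".

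The reminder rule is a single sentence in the Retention paragraph of 5.5: men are to be reached, by telephone or in another way they prefer, "prior to each MASLIHAT session or interview as a reminder". It names MASLIHAT sessions and interviews. TANSIHAT sessions are not mentioned, and no other section supplies a reminder for them.

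Session 1 has a special role. Under 5.2, index men are excluded if "they do not attend the first intervention session". Section 5.4 counts the same event as a screen failure, and 7.2 lists it as a reason for discontinuation from the study. Under 6.3, men learn their assignment when the group sessions are scheduled, so they know it before session 1.

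**The concern.** An attention control is there to equalise everything except content. If staff follow 5.5 as written, one arm gets a personal contact before every weekly session and the other gets none. Staff contact and session attendance could then differ by arm for a reason unrelated to what MASLIHAT teaches.

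Attendance carries weight in this plan. Besides the session-1 rule, 4.3 sets minimum attendance levels for evaluation, 4.4 requires at least four sessions for a man to count as having completed the study, and the dosage analysis in 9.4.2 uses attendance and its interaction with time and condition as predictors. A reminder rule that names one arm acts on that variable directly.

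**Working it through.** The plan states no reminder count and no session-1 attendance by arm, so there is no figure to reproduce. The check is a count of the contacts specified, followed by a comparison of the sections that bear on session 1.

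**Inputs**
- Sessions per index man: 5 in each arm (6.1.2).
- Interviews per man: 5, held "at baseline (prior to first intervention session), and at 3, 6, 9, and 12 months post-intervention" (8.1).
- Index men: 70 per arm (5.5).
- Reading of 5.5: the interview reminder is taken to apply to both arms, because the sentence is about participants in general. The session reminder is taken as worded.

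**Reminders specified per index man** = session reminders + interview reminders

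| | MASLIHAT | TANSIHAT |
|---|---|---|
| As written | 5 + 5 = 10 | 0 + 5 = 5 |
| As written, without the baseline interview | 5 + 4 = 9 | 0 + 4 = 4 |
| With both programmes named | 5 + 5 = 10 | 5 + 5 = 10 |

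Session reminders over a whole arm, as written: 70 × 5 = 350 in MASLIHAT against 70 × 0 = 0 in TANSIHAT. With both programmes named, there are 350 in each.

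**What follows from a missed first session**
- Against staying in: exclusion (5.2), screen failure (5.4), discontinuation (7.2), and groups that close to new members after session 1 (5.5).
- For staying in: rescreening may be considered, but only while the site's second group is unfilled (5.4). Men who consented but did not receive the intervention may be replaced (7.2); this restores the number, not the man.
- For the analysis: 9.3 includes everyone with a baseline interview, and that interview precedes session 1 (8.1). Section 9.4.2 includes men with at least one follow-up interview, which a man discontinued under 7.2 would not be expected to have. These statements pull in different directions.

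**Direction of any selection effect.** Let *d* be the share of an arm lost at session 1, *r* the risk in the whole arm and *r_L* the risk among the men lost. If they are not analysed, the observed risk is (*r* − *d* × *r_L*) / (1 − *d*). This falls as *d* rises when *r_L* > *r*, and rises when *r_L* < *r*. So if more men are lost from control, the comparison shifts against MASLIHAT when they are at higher risk than average, and in its favour when they are at lower risk. The documents give neither *d* by arm nor *r_L*.

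**The case against.** The strongest reply is that this is silence and not a decision. The sentence sits in a general retention paragraph, the pilot ran only MASLIHAT sessions (2.2), and the wording may simply have been carried over. The protocol also names the control inconsistently, as TANSIHAT, Healthy Lifestyle or control group, so one omitted name is thin evidence of intent. This stands: nobody can say from the text that control men will go without reminders. But staff work from the written rule, and the written rule names one arm.

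Second, the other attendance support covers both arms: notice at scheduling (6.3), transit passes (5.5), escort from subway stops (2.3.3), and tracing or rescheduling after a missed visit (5.5, 7.3). This also stands, and it limits the likely effect. Tracing, however, starts only after a visit is missed, which may be too late for a group that has closed.

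Third, five brief contacts are small beside five 2-hour sessions, interviewers are blinded (6.3), and in the pilot no participant missed more than one session (4.3). That makes a large effect on behaviour at 3 to 12 months unlikely, but it gives no reason to keep the difference.

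A reader might go further and infer any of the following. The documents do not support them.
- *Control men do receive less contact.* The text does not specify reminders for them; it does not withhold them.
- *The allowance of up to 150 screened for 140 enrolled gives the session-1 loss.* It is a ceiling on screening that also absorbs ineligibility and failure to recruit two network members.
- *Network members leave when their index man misses session 1.* No section removes them.
- *The bias favours MASLIHAT.* The direction depends on who is lost, as shown above.

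**Conclusion.** The point holds as a flaw in an operational rule. Section 5.5 specifies session reminders for one arm of a trial whose control is meant to match the other in attention. Read literally, the difference is 10 against 5 planned reminders per index man, or 9 against 4 without the baseline interview. The count assumes that interview reminders apply to both arms and that staff do no more than the text says.

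The consequence is an avoidable difference in staff contact and a possible difference in attendance. Session 1 is the sensitive place, because a miss there can remove a man after his assignment is known, subject to the rescreening and replacement routes and in tension with the intention-to-treat statement in 9.3. The effect on index men is direct. Network members attend no sessions and have interview reminders in both arms. No bias estimate can be given, and sample size, alpha and power are unaffected. The change is worth making because it is nearly free and removes the question.

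**What to change.** In the Retention paragraph of 5.5, extend the reminder rule to *each MASLIHAT or TANSIHAT session and each interview*, and state that the number, timing and mode of contact are the same in both arms. Report session-1 attendance by arm from the attendance records that facilitators already keep (6.4, 8.1).

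The cost is one phrase in the protocol, one line in the report, and up to five short reminder contacts for each of 70 control men (at most 350 in all) by existing staff. If control men are already being reminded in practice, the amendment only records it. How a missed first session is treated in 5.2, 5.4 and 7.2 should also be reconciled with 9.3, whatever is decided about reminders.
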